12.8 Early Termination Visit

The Early Termination visit will occur on the date the subject withdraws from the study, even if the date does not correspond to a protocol-specific visit.

If a subject leaves the study prior to the Week 260 visit, the subject will be asked to return to the study site and complete an Early Termination visit. At the Early Termination visit, as many of the following assessments as possible should be done:

- Physical examination
- Weight
- Assessment of Adverse Events and Concomitant Medications (including review of subject diary for bleeding and FVIII use)
- Vital Signs
- Blood chemistry, hematology, and coagulation tests (refer to Table 9.8.8.2.1)
- Urine Tests (refer to Table 9.8.8.2.1)

Page 108

- Liver Tests (refer to Table 9.8.8.3.1)
- FVIII Assays
 - o FVIII activity level (chromogenic substrate FVIII assay)
 - o FVIII activity level (one-stage clotting FVIII assay)
 - FVIII coagulation activity exploratory assay
 - o Bethesda assay (with Nijmegen modification) for FVIII inhibitor level
 - o FVIII protein assay
- AAV5 TAb Assay
- AAV5 TI Assay
- FVIII antibody titer
- Exploratory biomarker assessments
- PBMC collection
- VWF:Ag
- Direct Thrombin test
- TGA Assay
- PCR of vector DNA in blood, saliva, urine, semen, and stools
 - Sample testing at the ETV is not required if at least 3 consecutive samples were clear during the Post-Infusion Follow-Up period.
- Haemo-QoL-A assessment
- EQ-5D-5L
- HAL
- WPAI+CIQ:HS
- PROBE

12.9 End of Study

The study will end after the last subject yet to complete the last Long-Term Follow-Up visit (Week 260) does so, has transferred to another BMN 270 study, is withdrawn from the study, or discontinues from the study. BioMarin reserves the right to discontinue the study any time for clinical or administrative reasons and to discontinue participation of an individual Investigator or site for clinical or administrative reasons, including, but not limited to, poor enrollment or noncompliance with procedures of the protocol or GCP. In addition, the study

Page 109

may be terminated if, in the opinion of BioMarin, the safety of the study subjects may be compromised.

Page 110

13 DATA QUALITY ASSURANCE

BioMarin personnel or designees will visit the study site prior to initiation of the study to review with the site personnel information about the IP, protocol and other regulatory document requirements, source document requirements, eCRFs, monitoring requirements, and procedures for reporting AEs, including SAEs.

At visits during and after the study, a CRA will monitor the site for compliance with regulatory documentation, with a focus on accurate and complete recording of data on eCRFs from source documents, adherence to protocol, randomization (if applicable), SAE reporting and drug accountability records.

Data quality control and analysis will be performed by BioMarin or a designee, based on a predefined analysis plan.

Page 111

14 STATISTICAL METHODS AND DETERMINATION OF SAMPLE SIZE

14.1 Statistical and Analytical Plans

The statistical analysis plan (SAP) will provide additional details on the planned statistical analysis. Unless otherwise stated, all analyses will be performed using SAS.

14.1.1 Interim Analyses

An interim analysis is planned after approximately 20 evaluable HIV-negative subjects have completed the Week 26 visit (or have discontinued study participation prior to Week 26). Data will be reviewed by the DMC, based on the SAP, and a formal recommendation will be made whether to continue the study as designed.

The primary efficacy endpoint for the interim analysis involves hFVIII activity, as measured by chromogenic substrate assay, achieved post-BMN 270 infusion.

The fallback procedure (Wiens, 2005) will be used to adjust for multiplicity of the interim analysis at Week 26 and the final analysis at Week 52 (regardless of the interim analysis results, the study is planned to continue upon the DMC's recommendation, and the final analysis will be performed at Week 52). At the final analysis at Week 52, the secondary efficacy endpoints will be tested hierarchically; the level of significance will be determined by the fallback procedure.

The secondary and tertiary endpoints will be summarized descriptively at the interim (Week 26) analysis.

The details of the interim analysis, including the control of Type I error rate, will be specified in the SAP.

14.1.2 Procedures for Accounting for Missing, Unused and Spurious Data

Because the completeness of the data affects the integrity and accuracy of the final study analysis, every effort should be made to ensure complete, accurate, and timely data collection and, therefore, avoid missing data.

Missing data imputation and sensitivity analyses to assess the impact of missing data on the primary and secondary efficacy endpoints analyses are described in the following sections. Additional details regarding the handling of missing data will be provided in the SAP.

14.2 Primary Efficacy Endpoint

For the primary efficacy endpoint at Week 52 (ie, the change in the hFVIII activity during Weeks 49-52 post-BMN 270 infusion from baseline, as measured by chromogenic substrate

Page 112

assay), a one-sample t-test will be used to test the null hypothesis that the change is 0 or less against the alternative hypothesis that the change is greater than 0. Descriptive summaries of the proportions of subjects whose FVIII activity during Weeks 49-52 is greater than or equal to select thresholds, such as 15, 25 and 30 IU/dL, and the confidence intervals of the proportions will also be provided.

For a subject with a missing value of the primary endpoint, the median value in the subject's last 4-week window containing a valid observation will be used. Additional analyses will be conducted to examine the sensitivity of the results to the handling of missing data, including analysis using observed cases, and a mixed model for repeated measures (MMRM) approach. Further detail will be provided in the SAP.

The analyses for the primary endpoint will be performed using the analysis populations as defined in Section 14.8.

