Treatment of severe HA presently consists of intravenous injection of plasma derived or recombinant human FVIII protein (rhFVIII) concentrates both as prophylaxis 2-3 times per week, and at the time of a bleed, to prevent or control bleeding episodes, respectively. The half-life for FVIII (12 to 18 hours for most approved products) necessitates frequent infusions, and although a major advance in the treatment of HA, it remains common for severe HA patients to continue to have multiple bleeding events on prophylactic therapy (median ABR of 1-4 with prophylaxis treatment in a recently published retrospective observational study (Berntorp, 2017) and between 1-2 in 6 prospective FVIII interventional studies) and on-demand-only therapy (median ABR of 4.5-18 in a recently published retrospective study (Berntorp, 2017) and between 20-60 in 6 prospective FVIII interventional studies). The consequence of multiple bleeding events is the development of debilitating multiple-joint arthropathy and substantially increased risk of death. Chemical modification (eg, direct conjugation of polyethylene glycol (PEG) polymers) and bioengineering of FVIII (eg, FVIII-Fc fusion proteins) improve half-life by approximately 50%, and thus, show promise in reduced dosing and maintaining activity levels above 1% trough for a greater proportion of the dosing interval. However, these extended half-life FVIII variants remain dependent on multiple infusions to maintain critical levels of FVIII activity in severe HA patients. There is therefore a strong unmet need for a fully preventive treatment of HA to give patients a FVIII level compatible with a normal and hemorrhage-free life.

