Medical History	X			
Physical Examination ^a	X		X	X
Height and Weight	X			
Vital Signs	X	X	X	X
Assessment of Adverse Events and Concomitant Medications	X	X	X	X
Documentation of bleeding episodes and FVIII usage for previous 12 months (by either subject or clinical information)	X	X	X	
Distribution of subject diaries and training in their use ¹	X			
Electrocardiogram	X			
Liver Ultrasound	X			
hFVIII Assays ^b	X	X ^j	X	
AAV5 TAb Assays ^c	X	X	X	X
AAV5 TI Assay			X	
Screen for Hepatitis B, Hepatitis C, HIV ^d	X			
Blood chemistry, hematology, and coagulation tests ^e	X	X	X	
Fasting lipid panel (blood triglycerides, total cholesterol, HDL cholesterol, and LDL cholesterol)				X
Urine Tests ^e	X	X	X	
Liver Tests ^e	X	X	X	
PBMC collection (for baseline determination of AAV5 and FVIII specific cellular immunity)			X	

	Pric	or to BMN 270 Infusion		BMN 270
Assessment	Screening* (Day -28 to Day -1)	Smart Rescreening ⁱ (Day -28 to Day -1)	Baseline (Day -7 to Day -1)h	Infusion Visit (Day 1)k
Von Willebrand Factor Antigen (VWF:Ag)			X	
Direct Thrombin Activity Test ^g			X	
TGA Assay ^g			X	
PCR of vector DNA in blood, saliva, urine, semen, and stools			X	X
Biomarker testing ^f	X			
Exploratory biomarker assessments ^g			X	X
Haemo-QOL-A assessment			X	
EQ-5D-5L			X	
HAL			X	
WPAI+CIQ:HS			X	
PROBE			X	
BMN 270 Infusion				X
Hypersensitivity blood assessments ^m				X ^m

^{*} Screening assessments should be performed within 28 days of BMN 270 infusion (and must be performed within 42 days prior to BMN 270 infusion).

^a Complete physical examination should be done at Screening. Brief physical examination may be done at Baseline and at the BMN 270 Infusion Visit.

b Includes baseline FVIII activity (chromogenic substrate FVIII assay and one-stage clotting FVIII assay), coagulation exploratory assay, hFVIII inhibitor level (Bethesda assay with Nijmegen modification), hFVIII total antibody titer, and hFVIII protein assay. Baseline activity should be assessed at trough (at least >72 hours after last dose of replacement FVIII therapy, or 5x the known half-life of the FVIII concentrates administered).

^c Sample collection on the day of the infusion visit must be performed before the BMN 270 infusion is given. Screening, Smart Re-screening, and Infusion Day samples will be tested in a AAV5 TAb pre-screening assay specifically developed for enrolment purposes. Baseline and all post-dose samples will be tested in a different AAV5 TAb post-dose immunogenicity monitoring assay

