b Refer to Table 9.8.8.2.1 for laboratory assessments to be included, and to Table 9.8.8.3.1 for liver tests. LTs may be monitored more or less frequently (and in particular when ALT values are ≥1.5x ULN or > ULN & > 2x baseline value) based on discussion between the Medical Monitor and the Investigator and review of subject data, but LTs will be monitored at least twice weekly during periods when a subject's ALT is ≥ 3x ULN. Subjects with ALT ≥ 1.5x ULN or > ULN & > 2x baseline value during the study and either an alternative etiology considered or for further evaluation of the lab abnormality may undergo additional evaluations (eg, imaging studies including MRI or ultrasound, additional blood tests, and/or liver biopsy) at the discretion of the Investigator. Additional testing of FVIII and LTs during any study week may be performed if: (1) the ALT has increased to above ULN or increased by > 10 U/L from prior assessment; (2) Increases in ALT values from prior assessment are accompanied by declines in FVIII activity level; or after a discussion between the Medical Monitor and the Investigator based on discussion between the Medical Monitor and the Investigator.

c Includes FVIII activity level (chromogenic substrate FVIII assay and one-stage clotting FVIII assay), Bethesda assay (with Nijmegen modification) for hFVIII inhibitor level, coagulation exploratory assay, and hFVIII protein assay. If a subject has used FVIII within 72 hours of a measurement day, all efforts should be made to obtain FVIII activity measurements when a 72-hour interval without FVIII use is achieved; the 72-hour wash-out period is only intended for subjects who have achieved FVIII ≥ 5 IU/dL at 16 weeks after BMN 270 infusion and who have not resumed FVIII replacement therapy. If FVIII levels are elevated or stable over the course of several weeks, assessment of FVIII activity may be adjusted based on discussion between the Medical Monitor and the Investigator. A D-dimer may be considered under circumstances in which FVIII activity levels are above the normal physiological range and/or if there is a concern for a venous thromboembolism.

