9.8.2 Primary Efficacy Variables

9.8.2.1 FVIII Activity

The primary efficacy variable is change of the hFVIII activity, as measured by chromogenic substrate assay, during Weeks 49-52 post-BMN 270 infusion from baseline. Each subject's hFVIII activity during Weeks 49-52 is defined as the median of the values obtained during this 4-week window. Values for FVIII activity will be excluded if obtained within 72 hours since the last infusion of exogenous FVIII protein concentrates.

If a subject has used FVIII within 72 hours of a measurement day, all efforts should be made to obtain FVIII activity measurements when a 72-hour interval without FVIII use is achieved; The 72-hour wash-out period is only intended for subjects who have achieved

Page 70

FVIII \geq 5 IU/dL at 16 weeks after BMN 270 infusion and who have not resumed FVIII replacement therapy.

In the event of an FVIII activity level decline during the study:

- If FVIII activity has declined at least 20% from the peak but less than 35% and has declined for at least 2 consecutive assessments, FVIII activity and LTs should be repeated every 7 days until FVIII activity is stable or increasing
- If FVIII activity has declined >35% from the peak and has declined for at least 2 consecutive assessments, FVIII activity and LTs should be repeated every 72 hours until FVIII activity is stable or increasing

Note that fluctuations in FVIII activity are common, and if no clear trend indicating a decline in FVIII activity is observed, then this additional testing may be deferred (upon consultation between the Investigator and the Medical Monitor) until either a more clear trend of decline has been demonstrated or until the FVIII activity levels stabilize or increase.

Subjects who do not respond to BMN 270 treatment (ie treatment failure, manifesting as either failure to achieve FVIII activity ≥ 5 IU/dL by Week 52 or inability to maintain independence from prophylactic FVIII replacement therapy due to joint bleeding episodes, in the judgment of the Investigator) may, at the Investigator's discretion and after discussion with the Medical Monitor, follow an abbreviated visit schedule after Week 52 of the study by attending only the Q12W and End of Year visits during Years 2-5.

Details on collecting FVIII activity samples are included in the Laboratory Manual.

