9.8.3 Secondary Efficacy Variables

9.8.3.1 Factor VIII Replacement Therapy/Bleeding Episodes

Secondary efficacy variables are:

- Change of the annualized utilization (IU/kg) of exogenous FVIII replacement therapy during Week 5 to Week 52 post BMN 270 infusion from the baseline utilization of exogenous FVIII replacement therapy.
- Change in the annualized number of bleeding episodes requiring exogenous FVIII replacement treatment during Week 5 to Week 52 of the study post BMN 270 infusion from the baseline ABR.

Subjects must have high quality documented historical data available concerning previous bleeding episodes and exogenous FVIII usage over the previous 12 months in order to be eligible to enroll in the study. During the study, subjects will be asked at each study visit to report the use of factor replacement therapy and the number of bleeding episodes since the

Page 71

previous visit. This information will be captured on the subject's diary or other subject records.

Subjects are strongly encouraged to immediately consult Investigator for guidance regarding exogenous FVIII administration for suspected bleeds or bleeding episodes within the first 30 days post BMN 270 infusion.

In subjects who experience recurrent bleeding episodes, the Investigator and Medical Monitor will discuss whether to resume prior FVIII prophylaxis.

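### Carry-forward in Section 14.2 can score a subject who loses response and resumes prophylaxis with his earlier FVIII activity, biasing the mean change and threshold proportions upward

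*Protocol*

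**What the plan says.** The primary endpoint is the change from baseline in chromogenic FVIII activity, taken as the median of the values in Weeks 49-52. The rules that bear on it are these.

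- **Exclusion (Section 9.8.2.1):** "Values for FVIII activity will be excluded if obtained within 72 hours since the last infusion of exogenous FVIII protein concentrates".
- **Wash-out (Section 9.8.2.1; Table 9.1.4, footnote c):** the 72-hour wash-out is meant only for subjects with at least 5 IU/dL "at 16 weeks after BMN 270 infusion and who have not resumed FVIII replacement therapy".
- **Return to prophylaxis (Section 9.8.3.1):** "In subjects who experience recurrent bleeding episodes, the Investigator and Medical Monitor will discuss whether to resume prior FVIII prophylaxis". One limb of the treatment-failure definition in Section 9.8.2.1 is "inability to maintain independence from prophylactic FVIII replacement therapy due to joint bleeding episodes".
- **Imputation (Section 14.2):** where the primary value is missing, "the median value in the subject's last 4-week window containing a valid observation will be used". No exception is made for subjects who resumed prophylaxis or met the failure definition.
- **Sensitivity analyses (Section 14.2):** observed cases and an MMRM are named; further detail is left to the SAP.
- **Contrast (Section 14.3):** for annualized FVIII use, a missing change is set to 0, which means no benefit.

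**The concern.** Taken together, these rules make the primary value missing because the treatment stopped working, and then fill the gap with a measurement that may come from when it still worked. Neither named sensitivity analysis corrects this. Observed cases leaves these subjects out, and an MMRM predicts their late values from earlier ones under missing at random. Neither treats the missing value as a failure.

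What is at stake is estimation. The test against 0 is so heavily powered that the useful information lies in the size of the mean change and in the proportions reaching 15, 25 and 30 IU/dL. Those are the quantities that the rule can move, and only upward.

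**Working it through.** **Inputs from the protocol.** Prophylaxis is given "both as prophylaxis 2-3 times per week" (Section 7.3). Visits are every two weeks from Week 37, so Weeks 50 and 52 are the scheduled visits in the window (Section 12.6). N = 130, effect size 0.6, two-sided 0.05; Study 270-201 cohort 6E13 mean (SD) 103.8 (62.4) IU/dL, 95% CI 46.1 to 161.5; baseline 1 IU/dL (Section 14.7).

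**Assumptions, not in the protocol.** The fraction f of subjects who fail and lack a valid value is 5%, 10% or 20% (up to 30% for power). Their true Weeks 49-52 activity is 1 IU/dL. The carried value ranges from 5 to 103.8 IU/dL.

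**1. Reproducing the plan's figures.** With n = 7, the half-width is 2.447 × 62.4/√7 = 57.7, which gives 46.1 to 161.5 as stated. The effect size at the lower limit is (46.1 − 1)/62.4 = 0.72, against the stated 0.7. The one-sample t-test with N = 130 has noncentrality 0.6 × √130 = 6.84 and power above 99.99%, consistent with the stated minimum of 95%.

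**2. Chance of no valid value after resumption, visits timed at random.**
- Three infusions a week: gaps of 56 h, or 48/48/72 h. No time lies beyond 72 h, so the chance is 100%.
- Two infusions a week: gaps of 84 h give (84 − 72)/84 = 1/7 of the time beyond 72 h; gaps of 72/96 h give 24/168 = 1/7. The chance at two visits is (6/7)² = 0.735, about 73%. If a third visit falls in the window through the ±1 week allowance, it is (6/7)³ = 0.63.

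**3. Overstatement of the mean change.** This is f × (carried value − true value), in IU/dL:

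| f | carried 5 | carried 15 | carried 46.1 | carried 103.8 |
|---|---|---|---|---|
| 5% | 0.2 | 0.7 | 2.3 | 5.1 |
| 10% | 0.4 | 1.4 | 4.5 | 10.3 |
| 20% | 0.8 | 2.8 | 9.0 | 20.6 |

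**4. Overstatement of the proportions.** Each such subject can turn at most one non-responder into a responder, so each proportion is overstated by at most f.

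**5. Power if failures are set to change = 0.** With responder mean μ and SD σ, the mixture has mean (1 − f)μ and variance (1 − f)σ² + f(1 − f)μ². For μ/σ = 0.6 and f = 30%, the mean is 0.42, the variance is 0.70 + 0.21 × 0.36 = 0.776 and the effect size is 0.42/0.881 = 0.48. The effect sizes at 5%, 10%, 20% and 30% are 0.58, 0.56, 0.52 and 0.48. Power is at or above 99.97% throughout.

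**6. The other reading of the wash-out sentence.** If it is taken to lift the 72-hour exclusion for subjects who have resumed, their values would include infused FVIII. That also biases upward, so the ambiguity offers no protection.

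**The case against.** The strongest reply is that the size is unknown and may be small. Prophylaxis is reconsidered after recurrent bleeding, FVIII is sampled every one or two weeks, and declines prompt extra sampling. The last valid window may therefore already show the loss. At a carried value of 5 IU/dL the overstatement is under 1 IU/dL even with 20% failures. This stands as a limit on size. It does not remove the problem: the Amendment 3 summary of changes bases resumption on clinical grounds and says that a need tied to an activity level is not established, so nothing ensures a low carried value.

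A second reply is that the SAP may add analyses. It may, but Section 14.2 itself fixes the primary imputation. It is also true that resumed prophylaxis appears in annualized FVIII use, so loss of response is not invisible in the trial as a whole; it is the primary endpoint that can miss it.

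Some stronger readings that a reader might infer are not supported:

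- **That every such subject lacks a value.** At two infusions a week about 27% would have one at two random visits, and trough sampling could raise that. A stray valid sample after resumption could also supply the carried window.
- **That all failures inflate the result.** Never-responders carry a low value.
- **That all withdrawals should count as no change.** Early termination includes FVIII assays (Section 12.8), and a subject may leave for unrelated reasons with good activity.
- **That the 72-hour exclusion conflicts with the baseline rule.** Table 9.1.1, footnote b asks for "at least >72 hours after last dose of replacement FVIII therapy, or 5x the known half-life of the FVIII concentrates administered". The two conditions are alternatives, so more than 72 hours alone satisfies it and no mismatch is shown.

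**Conclusion.** The point holds as a bias in estimation. The primary carry-forward rule, combined with the 72-hour exclusion, can credit subjects who lost response and resumed prophylaxis with earlier, higher activity. The direction follows from the protocol's own text. The size does not: it runs from about 0.2 IU/dL (5% failures, carried value 5) to about 20 IU/dL (20% failures, carried value at the 270-201 mean), with a true value of 1 assumed throughout. The upper end supposes no decline at all before resumption. A reader might infer that the primary test is compromised; it is not, since power barely moves even with 30% of subjects set to no change.

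**What to change.** In Section 14.2, state that when the Weeks 49-52 value is missing because the subject resumed prophylaxis or met the protocol's treatment-failure definition, the baseline value is used in the primary analysis: change = 0 and below every threshold. Keep the last-valid-window rule for these subjects as a sensitivity analysis. Withdrawals unrelated to failure need not be set to change = 0. Define resumed prophylaxis so that the isolated use allowed in Section 9.4.8.1, such as peri-operative cover, does not trigger the rule.

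In Sections 9.8.2.1 and 14.2, say explicitly that the 72-hour exclusion still applies to values from subjects who have resumed FVIII. The length of the exclusion window need not change.

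The cost is wording only, since the 72-hour exclusion already requires exogenous FVIII use to be recorded. The mean change and threshold proportions may come out slightly less favourable. In return, the primary endpoint would follow the same no-benefit principle that Section 14.3 applies to FVIII use.
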